Stroke is a leading cause of long-term disability worldwide, often resulting in cognitive impairments, particularly in attention, which can significantly affect patients' quality of life and daily functioning. Evidence suggests that music therapy can enhance cognitive recovery during neurorehabilitation by engaging multiple brain networks and promoting neuroplasticity. While home-based rehabilitation has demonstrated effectiveness post stroke, there is limited evidence regarding the feasibility and impact of music therapy delivered at home for stable stroke patients. Furthermore, no studies have examined the efficacy of structured music therapy as part of a cognitive rehabilitation program in Malaysia, despite efforts over the past decade to promote music for therapeutic purposes. Unlike in other countries where music therapy is an established neurorehabilitation modality, it has not been formally incorporated into most local neurorehabilitation programs. This study proposes to investigate the effects of home-based music therapy on cognitive functions in stroke patients in Malaysian setting. If successful, this approach could support the integration of music therapy into clinical neurorehabilitation home-based settings, promoting its wider use for cognitive recovery post-stroke.

OBJECTIVES/OUTCOMES**Objectives:**

1. To determine the feasibility and acceptability of a structured home-based music therapy rehabilitation programme for improving attention and processing speed among stable stroke survivors in Malaysia, as measured by recruitment rate, adherence, retention, and participant satisfaction.
2. To explore the preliminary effects of the home-based music therapy rehabilitation programme on attention and processing speed in post-stroke patients using standardized cognitive outcome measures.
3. To assess the safety and practicality of implementing a home-based music therapy rehabilitation intervention, including monitoring adverse events, caregiver involvement, and compliance with the prescribed programme.

Expected outcomes:**1. Feasibility and Acceptability**

It is expected that the home-based music therapy rehabilitation programme will demonstrate acceptable feasibility among stable stroke survivors in Malaysia. This includes achieving satisfactory recruitment and retention rates, good adherence to the prescribed intervention, and positive participant-reported satisfaction. These outcomes will indicate that the programme is acceptable and practicable for implementation in a home setting within the local context.

2. Preliminary Cognitive Outcomes

The study is expected to show trends toward improvement in attention and processing speed following participation in the home-based music therapy rehabilitation programme, as measured by standardized cognitive assessment tools. While the study is not powered to determine definitive efficacy, the findings will provide preliminary data on potential cognitive benefits and inform the selection of outcome measures and effect size estimates for future larger-scale trials.

3. Safety and Practicality

The intervention is expected to be safe, with minimal or no adverse events related to participation. It is anticipated that participants and caregivers will be able to implement the programme with minimal difficulty, demonstrating adequate compliance with the prescribed activities. These findings will support the practicality of delivering a structured music therapy rehabilitation intervention in a home-based setting.

METHODOLOGY

Study design

This study will adopt a prospective, single-centre, randomized controlled feasibility study design with two parallel groups: an intervention group receiving music therapy in addition to standard neurorehabilitation, and a control group receiving only standard neurorehabilitation. The primary focus is to evaluate the feasibility, acceptability, and safety of a structured home-based musical rehabilitation programme for cognitive rehabilitation after stroke. Secondary objectives include exploration of preliminary effects on attention and processing speed.

Patients with a history of stroke who are admitted to, or attending follow-up at, University Malaya Medical Centre (UMMC) during the study period will be screened for eligibility. Eligible patients will be approached and provided with detailed information about the study and invited to participate. In addition, public advertisements (posters and flyers within UMMC) will be used to increase awareness of the study and facilitate recruitment. Patients who meet the inclusion criteria and agree to participate will be enrolled only after providing written informed consent.

Following enrolment, all participants will be allocated to either an intervention group or a control group in a 1:1 ratio. To ensure that there are exactly 20 patients in both the control and intervention groups, block randomization will be used using a random number generator. After randomization, the group assignments will be kept in a password-protected file that only the study coordinator can access. The assessor will not have access to this information because the patients will be labelled with anonymous codes that do not reveal whether they are in the control or intervention group. The assessor will only know the code, not the group assignment, ensuring unbiased evaluation.

A certified music therapist will prescribe the intervention and train the patients and caregivers before the start of the home-based music therapy. A trained assessor will evaluate the cognition at baseline, and also the outcome. The assessor is blinded to the patients' allocation group and will evaluate the cognitive outcomes at baseline, immediately after completion of the intervention period at four weeks and at 3 months post intervention.

Intervention group

The music therapy session described follows a structured and engaging approach, aimed at enhancing the patient's cognitive skills. Here's a summary of the session components:

Intervention Group: Home-Based Music Therapy Rehabilitation Program

1. Song Materials and Levels

The song materials selected for this research will be sourced from copyrighted compositions under UM Centre of Innovation and Enterprise (UMCIE). This maximizes the utilization of readily available resources and serves as a platform for promoting the original works of UM lecturers. The songs are organised into three difficulty levels, with approximately five songs per level. Songs within each level have equivalent rhythmic and cognitive demands, allowing variation without altering task difficulty.

2. Baseline Assessment for Music Therapy

Participants will undergo an initial level assessment conducted at the hospital by the trained music therapist. If travel is not feasible, level assessment is conducted at the participant's home. The songs will be presented to the participants and they will choose one song to start.

To ensure the safety of the research therapist conducting home-based assessments, a multi-layered safety protocol will be implemented for all home visits:

- a) a designated co-investigator will act as a safety contact. Before any home visit, the therapist will provide this contact with a full schedule, including the participant's address and the expected duration of the visit.
- b) the therapist will then follow a mandatory check-in procedure via text message:
 - Pre-departure: A message before leaving for the visit
 - Arrival: A message upon safely arriving at the participant's home
 - Departure: A message upon leaving the participant's home
 - Safe Return: A final message upon returning to a safe location.

Escalation Protocol:

If the safety contact does not receive the final "safe return" message within an agreed-upon time, they will first attempt to contact the therapist directly. If unsuccessful, they will then call the participant/caregiver. If contact cannot be established with either party, the safety contact will be authorised to contact the relevant local authorities to conduct a wellness check.

Confidentiality Protocol for Unofficial Recordings by Family Members

To protect participant confidentiality and the integrity of the research data, the following protocol will be implemented to address the possibility of family members or caregivers making personal recordings during home-based sessions:

1. Enhanced Informed Consent:

The Participant Information Sheet (PIS) and Consent Form will include a specific clause addressing this issue. During the consent process, the investigator will explicitly discuss the following with both the participant and the caregiver(s):

Purpose of Official Recordings: A clear explanation that the researcher's video recordings are for official data collection and analysis purposes only and will be stored securely according to the university's data protection policies.

Prohibition of Unofficial Recordings: A verbal and written request that family members and caregivers refrain from taking any personal photos, videos, or audio recordings during the structured assessment and intervention sessions.

Rationale: An explanation that this is to protect the participant's privacy and the integrity of the research data, as unofficial recordings are not covered by the study's ethical approval or data security protocols.

The following statement will be added to the consent form, requiring a separate signature or initials from the participant and/or legally authorised representative:

"I understand that the research team will video record the sessions for assessment and data analysis purposes only. I agree that I, and any family members or caregivers present, will not take any personal photographs, video recordings, or audio recordings during these sessions. I understand that any unauthorized recording would be a breach of the participant's confidentiality."

Pre-Session Reminder:

At the beginning of each home visit, the research therapist will provide a friendly, verbal reminder to everyone present (participant, family members, caregiver) about the confidentiality agreement and the request to refrain from using personal mobile phones or other devices to record the session.

3. Participant and Caregiver Training

At the beginning of the intervention, both participants and caregivers will undergo a structured training conducted by the music therapist to ensure they can independently carry out the program at home. The song chosen for the training will be different than the songs they will use during the home-based therapy rehabilitation program.

4. Caregiver Guidelines and Checklist

Caregivers are provided with written guidelines and a structured monitoring checklist to support adherence, safety monitoring, and documentation throughout the intervention.

5. Attentional Priming

Each session begins with 3–5 minutes of focused listening, during which participants will be instructed to observe and listen attentively to the musical compositions generated by the Finale music software. The software's user-friendly interface will display a tempo line adorned with pertinent remarks and symbols, providing clear guidance for the patients to follow.

An Eight-Tone Desk Bell (Figure 1) will be integrated with the Finale music software (Figure 2), enabling stroke patients to observe and listen to musical compositions generated.

6. Rhythm–Action Training

Participants will actively engage with the music and synchronise tapping on an Eight-Tone Desk Bell. The rhythmic and visual cues will be displayed on the Finale software interface, targeting processing speed, sustained attention, and sensorimotor integration.

7. Session Dosage and Frequency

Each session lasts 40 minutes and is conducted daily for five days per week, in accordance with rehabilitation literature. Session duration and frequency are recorded in the caregiver checklist.

8. Progress Monitoring and Adjustment

Progression is guided by bi-weekly level assessments by the music therapist at their homes. Adjustments made based on participant performance and endurance on the songs chosen earlier. The adjustments will include either changing the song within the same difficulty level or change to the songs in the next level of difficulty.

9. Adherence Monitoring

Caregivers will complete the checklist after each session, documenting completion, duration, participant alertness, and signs of fatigue. Weekly therapist phone call follow-ups support adherence and address concerns.

Control Group: Standard Care

Participants in the control group continue with usual standard neurorehabilitation program as prescribed by the rehabilitation team, without exposure to the music-based intervention.

This will provide a baseline to compare outcomes with the intervention group and evaluate the feasibility and preliminary effects of the music therapy intervention. The usual cognitive rehabilitation program during the subacute stroke period focuses on restoring cognitive abilities

such as attention, memory, executive functions, and communication. The key components typically include:

1. **Attention Training:** Exercises that improve sustained, selective, and divided attention, crucial for regaining concentration in daily activities.
2. **Memory Aids:** Tools like mnemonic strategies, repetition tasks, and external memory aids (e.g., calendars, notes) help rebuild short-term and working memory.
3. **Executive Function Training:** Targeting skills such as problem-solving, planning, and organizing tasks through structured exercises, gradually improving independent thinking.
4. **Communication and Language Therapy:** Speech-language pathologists work with patients to improve verbal and non-verbal communication, focusing on both comprehension and expression.
5. **Problem-Solving Exercises:** These help patients break down real-life problems into smaller, manageable steps, encouraging better decision-making skills.

Both the intervention and control groups will continue receiving the standard care

Figure 1. Eight-Tone Desk Bell

[figure not shown]

Figure 2: Finale Music Software User Interface

Inclusion Criteria:

1. Diagnosed with ischemic or haemorrhagic stroke confirmed by CT scan
2. Duration of stroke within the first one year
3. Age 18 – 70 years old
4. Ability to provide informed consent
5. Understands Bahasa Melayu or English with basic communication abilities to follow instructions during therapy sessions
6. Mild to moderate cognitive impairments with MoCA score of 10-25, with incomplete score for the attention sections
7. Availability of caregiver (formal or informal) who can assist in the music therapy, monitor and give feedback during the music therapy sessions at home
8. Have one normal functioning hand to perform the movements during the music therapy rehabilitation program
9. Have good balance and able to sit upright

Exclusion Criteria:

1. Severe aphasia
2. Significant uncorrected hearing or visual impairments preventing engagement in music therapy.
3. Severe or unstable medical conditions (e.g., uncontrolled hypertension or diabetes).
4. Medications that significantly impair cognition or motor function (e.g., high-dose sedatives).
5. History of neurological diseases other than stroke (eg, Parkinson's disease).

Outcome measures

This will be assessed at baseline, after completion of 4-week sessions and also at 3 months after completion. Primary outcome measures are Montreal Cognitive Assessment (MoCA), Trail Making Test (TMT A and B), Digit Span (Forward and Backward) and Clock Drawing Test (CDT). The secondary outcome measure is computer-based Cogniplus software for Reaction Time and Attention tests

Sample size calculation:

A sample of 40 subacute stroke patients (18 control and 18 intervention) within the first one year post-stroke, will be recruited from UMMC. This number is chosen based on practical considerations to evaluate feasibility metrics and exploratory analysis as in the objectives. For these purposes, a sample size of 36 is typically adequate to gather enough information about the practical aspects of the trial. This number could also ensure that the feasibility objectives are met even with at least 20% dropouts. This total number of 36 will be sufficient within the study period and the grant duration.

Statistical Analysis:

Descriptive Statistics and Exploratory Inferential Statistics will be used in this study.

The means, standard deviations, and 95% confidence intervals (CIs) for cognitive outcome measures (e.g., memory, attention, executive function scores) at baseline, post-intervention, and follow-up will be used. This will provide a preliminary understanding of the data distribution and effect sizes.

For the exploratory Inferential Statistics, independent t-test (or Mann-Whitney U Test) will be used to compare the mean changes in cognitive scores between the intervention and control groups. The independent t-test if the data are normally distributed. If not, we will use the Mann-Whitney U test as a non-parametric alternative.

Within each group, we will compare the baseline and post-intervention scores using the paired t-test for normally distributed data or the Wilcoxon signed-rank test for non-parametric data. Cohen's d will be used for independent t-tests (between groups) or r for non-parametric tests.

A repeated measures ANOVA (if the data is normally distributed) or a mixed-effects model will be used to explore changes over time (baseline, post-intervention, and follow-up). Given the small sample size, these analyses will likely be underpowered but can provide estimates of variability and preliminary trends.

RESEARCH DATA

Where will the data be kept?

The demographic data of the patients, and data on cognitive performance and other relevant data will be kept in a dedicated research file and hard drive. The files are in the laptop will be secured with password and the notes will be kept in a locker in the Department of Rehabilitation Medicine, Faculty of Medicine with one of the co-researchers.

Anonymity of data

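### Time since stroke may range up to one year with no minimum, yet neither the between-arm comparison nor the randomisation takes it into account, which costs precision and leaves the planning estimate open to chance imbalance

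*Protocol*

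**What the plan says.** - **Entry.** Inclusion criterion 2 reads "Duration of stroke within the first one year", with no lower limit. The Study design section recruits both inpatients and patients attending follow-up. The first objective speaks of patients "among stable stroke survivors in Malaysia", and the sample size section of "A sample of 40 subacute stroke patients (18 control and 18 intervention) within the first one year post-stroke". Neither term sets a minimum time, and the second is itself extended to one year.
- **Allocation.** The Study design section states that "block randomization will be used using a random number generator". The only purpose given is "To ensure that there are exactly 20 patients in both the control and intervention groups". No stratification or minimisation factor is named anywhere in the Protocol.
- **Analysis.** The Statistical Analysis section compares mean change in cognitive scores between arms by an independent t-test, or by Mann-Whitney if the data are not normal, without a covariate. The repeated measures ANOVA or mixed model is described only as exploring change over time, and no term for time since stroke is named.
- **Use.** Under Preliminary Cognitive Outcomes, the findings are to "inform the selection of outcome measures and effect size estimates for future larger-scale trials".

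**The concern.** A patient a few weeks after stroke and one near the end of the first year can be expected to differ in how much cognition improves without added treatment. The documents give no recovery rates, so this is a plausible premise and not a figure taken from the plan. If it holds, time since stroke is a predictor of the outcome that neither the allocation nor the stated test uses.

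Two things follow. The variation between early and late patients stays in the error term and widens the interval. And if one arm happens to receive more early patients, its mean change moves for a reason unrelated to music. Adjusting for the baseline score alone would not deal with this, because patients with equal scores at different times after stroke may have different recovery ahead of them. What is at stake is the effect size carried into a later trial; the feasibility outcomes are hardly touched.

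**Working it through.** **Inputs from the Protocol:** 1:1 allocation; 20 per arm (Study design) or 18 per arm (sample size section); unadjusted comparison of change. No power, SD, early share or recovery rate is stated, so there is no figure of the plan's own to reproduce on this point.

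**Assumptions:** 30–50% of patients are early (for example, within 3 months of stroke); early patients gain 0.5 to 1.0 residual SD more than late ones.

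**1. Chance of imbalance.** With *K* early patients among 40 and 20 per arm, the early count in one arm is hypergeometric. The SD of the difference in early share is √[p(1−p) × (40/39) × (2/20)], with p = *K*/40.

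| Early patients *K* | SD of difference in share | P(arms differ by ≥ 4 early patients) |
|---|---|---|
| 12 (30%) | 0.147 | 0.301 |
| 16 (40%) | 0.157 | 0.333 |
| 20 (50%) | 0.160 | 0.343 |

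With *K* even, the arms can differ only by an even number, which favours the threshold of four. If *K* is left to vary, with each patient early with probability 0.3, 0.4 or 0.5, the exact probabilities are 0.226, 0.258 and 0.268 (0.22, 0.26 and 0.27 by simulation). Hence about 22–34%. Blocks of four do not help: simulated with *K* fixed, they again give 30–34%. At 18 per arm, the chance of a difference of at least four is 0.146, 0.305 and 0.318 for 11, 14 and 18 early patients.

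**2. Size of the shift.** Four patients in 20 is 0.20. The shift is 0.20 × 0.5 = 0.10 SD to 0.20 × 1.0 = 0.20 SD.

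**3. Yardstick.** With residual SD 1, the standard error of the arm difference is √(2/20) = 0.316, and the 95% half-width is 1.96 × 0.316 = 0.62. The shift is therefore about one third to two thirds of one standard error.

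**4. Precision lost.** Left unadjusted, with 50% early, the variance becomes 1 + g² × 0.25 × 40/39 for a recovery gap of g SD. The standard error is 0.326 for g = 0.5 (3% larger) and 0.354 for g = 1.0 (12% larger).

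**5. What each remedy gains.** 10,000 simulated trials, 20 per arm, 50% early, true effect 0.8 SD, early/late indicator as the covariate:

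| Approach | Power, g = 0.5 | Power, g = 1.0 |
|---|---|---|
| As planned | 66% | 59% |
| Stratified, unadjusted test | 66% | 60% |
| Adjusted only | 68% | 68% |
| Stratified and adjusted | 68% | 69% |

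**6. Error rates.** With no true effect, the planned test rejects in 5.0% of trials over all randomisations. Among trials where the early share is at least 20 points higher in the music arm, it rejects in favour of music in 5.7% (g = 0.5) or 6.8% (g = 1.0), against a nominal 2.5%. Stratifying while keeping the unadjusted test makes it conservative: about 4% (g = 0.5) or 3% (g = 1.0).

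**The case against.** Unstratified blocks are a valid design for a single-centre feasibility trial of 40, and the Protocol says plainly that efficacy is exploratory and underpowered. Stroke type, age or MoCA score could be proposed as strata just as easily. Covariates are often left to a statistical analysis plan, and one may exist. The early share, the cut and the recovery gap are all assumed, and the resulting shift is smaller than one standard error.

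Most of this stands as a limit on size. It does not remove the point, because the Protocol names the between-arm test and it is unadjusted, and because allocation cannot be redone after enrolment. The objection also shows where the remedy belongs: the covariate does nearly all the work, and stratification alone does almost none.

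Two stronger readings are tempting and are not supported. A reader might infer that patients enter from the first day after stroke. The criterion sets no minimum, but it does not say that, and consent, sitting balance, exclusion of unstable conditions and home delivery make it unlikely. A reader might also infer that the design is biased towards finding a music effect. It is not: the imbalance is equally likely in either direction, and the overall error rate is nominal. The distortion is conditional on the allocation drawn.

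**Conclusion.** The point holds as a moderate, cheaply corrected weakness in a stated method. Under the assumptions above, about one trial in five to one in three would have arms of 20 differing by four or more early patients. A difference of four moves the estimate by 0.10–0.20 SD against a standard error of about 0.32 SD, and ignoring the variable inflates that standard error by about 3% to 12%. If the recovery gap is smaller than 0.5 SD, the effect shrinks in proportion. The feasibility, acceptability and safety conclusions do not depend on it.

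**What to change.** 1. **Main change, Statistical Analysis section.** Replace the unadjusted between-arm comparison with a linear model (ANCOVA, or the mixed model already mentioned) containing arm, baseline score and time since stroke at randomisation, with the form of the last term fixed in advance. The stroke date is already needed to check inclusion criterion 2.
2. **Second step, Study design section.** Form the permuted blocks within two strata of time since stroke, with the cut chosen by the sponsor before the first randomisation. Do this only together with step 1, since stratifying under the unadjusted test gains almost nothing.

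**Cost.** One or two degrees of freedom and a second randomisation list; no added patients or visits. An incomplete last block in each stratum means the totals may end at 19/21 or, with blocks of four, occasionally 18/22. The wording that promises exactly 20 per arm would have to be relaxed accordingly.

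### Safety is part of the primary focus, but no described procedure systematically asks about or records adverse events in either arm

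*Protocol*

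**What the plan says.** Under Study design the protocol states: "The primary focus is to evaluate the feasibility, acceptability, and safety of a structured home-based musical rehabilitation programme". Objective 3 is to assess safety and practicality, "including monitoring adverse events, caregiver involvement, and compliance with the prescribed programme". Under Expected outcomes, item 3, the anticipated result is already given: "The intervention is expected to be safe, with minimal or no adverse events related to participation".

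The procedures bearing on this are all in the description of the music arm:

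- Item 4 provides caregivers with a "structured monitoring checklist to support adherence, safety monitoring, and documentation throughout the intervention".
- Item 7 adds: "Session duration and frequency are recorded in the caregiver checklist".
- Item 8: "Progression is guided by bi-weekly level assessments by the music therapist at their homes".
- Item 9: "Caregivers will complete the checklist after each session, documenting completion, duration, participant alertness, and signs of fatigue". It continues: "Weekly therapist phone call follow-ups support adherence and address concerns".

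The control-group section describes usual neurorehabilitation and no study record. The Outcome measures section names MoCA, Trail Making, Digit Span and Clock Drawing as primary and the Cogniplus tests as secondary, at baseline, after the 4-week programme and 3 months later. The Statistical Analysis section deals with cognitive scores only.

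**The concern.** The trial sets out to say something about safety, but the text never reaches the step where a participant or caregiver is asked whether an adverse event occurred and the answer is written down. There is no definition, no schedule of enquiry and no form described. The instrument assigned to safety monitoring has stated contents that cover adherence and tolerability.

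Two consequences follow. A count at or near zero, which is the result the protocol expects, could arise because few events happened or because few were asked about, and the data could not tell these apart. A count above zero would be hard to read too. People within a year of a stroke have events whatever they are assigned to, and without the same enquiry in controls there is no background rate to set the count against.

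This belongs in the protocol and is not a detail for an analysis plan. What is collected, when and in which arm has to be settled before recruitment, and no later analysis can recover events that nobody asked about.

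**Working it through.** **Comparing the text.** The protocol gives no adverse-event rate, threshold or power, so there is no figure of its own to reproduce. The first check is to go through each described contact or record and see whether it is said to ask about or record adverse events.

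| Contact or record | Arm | Stated purpose or content | Adverse events stated? |
|---|---|---|---|
| Caregiver checklist (items 4, 7, 9) | Music | Completion, duration, frequency, alertness, fatigue; safety monitoring as a general purpose | No item listed |
| Weekly phone call (item 9) | Music | Adherence and concerns | No |
| Bi-weekly home visit (item 8) | Music | Level assessment and song adjustment | No |
| Video recording (consent text) | Sessions recorded by the research team | Assessment and data analysis | No |
| Assessments at 4 weeks and 3 months | Both | Cognitive tests | No |
| Usual rehabilitation | Both | Clinical care | No study collection described |

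The only contacts the study itself describes in both arms are the cognitive assessments, and these carry no safety question.

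**Illustrating what incomplete collection does.** Inputs from the protocol: 5 sessions a week for 4 weeks, so 5 × 4 = 20 sessions per participant. The music arm has 20 participants under Study design or 18 under Sample size calculation. That conflict is a separate matter, so both are shown. The arm therefore produces 18 × 20 = 360 to 20 × 20 = 400 sessions. Assumed, not in the protocol: a true rate p of participants with at least one event, and a fraction c of affected participants who are recorded.

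Chance of recording at least one affected participant = 1 − (1 − cp)^n. With p = 10%:

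| Fraction recorded | n = 18 | n = 20 |
|---|---|---|
| All (c = 1) | 1 − 0.90^18 = 85% | 1 − 0.90^20 = 88% |
| Half (c = 0.5) | 1 − 0.95^18 = 60% | 1 − 0.95^20 = 64% |
| A quarter (c = 0.25) | 1 − 0.975^18 = 37% | 1 − 0.975^20 = 40% |

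With a quarter recorded, the trial reports no events 63% (n = 18) or 60% (n = 20) of the time although the true rate is 10%. With all recorded, those figures are 15% and 12%.

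**What zero events would mean with full collection.** The exact two-sided 95% upper limit is 1 − 0.025^(1/n): 18.5% for n = 18 and 16.8% for n = 20. Allowing for the 20% dropout named under Sample size calculation, 18 × 0.8 = 14.4 (take 14) gives 23.2%, and 20 × 0.8 = 16 gives 20.6%. These limits come from the small sample and would be the same after the fix. They are needed for reporting but do not measure the defect.

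**The case against.** The best defence is that the protocol does arrange to observe participants. Inclusion criterion 7 requires a caregiver able to monitor and give feedback. Alertness and fatigue, recorded after each session, are tolerability signals. The weekly call deals with concerns, the therapist visits the home, and some or all sessions are on video. A serious event would probably surface through one of these routes or as missed sessions. The checklist form is not shown, and the list under Adherence Monitoring is plainly not complete, since item 7 adds frequency. The safety objective concerns the music programme, and no comparison between arms is promised.

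Much of this stands, and it rules out three stronger readings. A reader might infer that the checklist is the only session record and that the trial is not looking for harm at all. The video, calls and visits contradict that, and an unseen form cannot be said to lack an item, only to have none listed. A reader might infer that controls have no contact before 4 weeks and that their events would be wholly missed. In fact they continue usual rehabilitation and are seen at the study assessments. A reader might also fault the trial for an invalid between-arm safety analysis, but none is stated.

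The defence does not supply a systematic enquiry. Each route is an opportunity to hear of an event, and none is described as a means of asking for or recording one. If the form does hold an adverse-event item, that would close part of the gap in the music arm but leave the controls as they are.

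**Conclusion.** The point holds in this form. Safety is a primary focus and adverse-event monitoring is an objective, but no described procedure systematically elicits or records adverse events, and no study collection is described for controls. As written, the trial could not soundly support the conclusion it expects to reach on safety.

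The size cannot be fixed from the documents, because the fraction of events that informal contact would pick up is unknown. Under the assumptions shown (true rate 10%, between a quarter and all of affected participants recorded), the chance of a false impression of no events runs from 12–15% up to 60–63%. The conclusion rests on the protocol text alone. It should be corrected before recruitment, though it does not affect the cognitive outcomes.

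**What to change.** 1. Define adverse events and list them as a safety outcome in the Outcome measures section.
2. At the existing 4-week and 3-month assessments, ask participants in both arms the same structured adverse-event questions. Someone other than the blinded cognitive assessor should ask them. Base any listing by arm (participants with at least one event, with an exact 95% confidence interval) on these shared-visit answers only.
3. Add an adverse-event item to the caregiver checklist and a standard question to the weekly call. Report what they yield separately, as a descriptive tolerability record for the music arm. Pooling these reports with the shared-visit answers would inflate the music-arm count, because controls have neither checklist nor call.
4. If no events are seen, report the two-sided exact upper limit for the number actually assessed (18.5% for 18, 16.8% for 20, before dropout).

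The cost is one checklist line, one call question and a few minutes at visits that already take place. One weakness remains: the person asking may know the allocation (the study coordinator, for instance, holds the allocation file), and this should be stated as a limitation.
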